2. **Adherence.** For both groups, proportion of medication course completed will be recorded
3. **Time to initiation of medications.** For both groups, time to initiation of anti-hypertensive medications will be tracked
4. **Final plan at 6 weeks.** For both groups, continuing medication regimens at 6 weeks will be collected.
5. **Hospital readmissions.** Hospital readmission for any indication will be collected for both groups
6. **Triage/ED visits.** Presentation to the obstetric triage unit or the emergency department for any indication will be collected for both groups
7. **Maternal morbidity and mortality.** Incidences of eclampsia, stroke, PRES, maternal death will be collected for both groups
8. **Breastfeeding continuation.** Rates of breastfeeding continuation will be collected for both groups
9. **Adverse effects.** Incidences of hypotension, electrolyte abnormalities, and development of renal insufficiency will be collected for both groups.

2.3.8 Definitions

Chronic hypertension will be defined according to ACOG guidelines as blood pressure measurement of EITHER ≥ 140 mm Hg OR diastolic ≥ 90 mm Hg on at least 2 occasions, at least 4 hours apart, prior to 20 weeks gestation.²

Hypertensive disorders of pregnancy will be defined according to ACOG guidelines.² The minimum criteria for a diagnosis of HDP are as follows:

- Blood pressure measurement of EITHER systolic ≥ 140 mm Hg OR diastolic ≥ 90 mm Hg on at least 2 occasions, at least 4 hours apart, between 20 weeks gestation and delivery
- Blood pressure measurement of EITHER systolic ≥ 160 mm Hg OR diastolic ≥ 110 mm Hg on at least 2 occasions qualifies as severe features

Diagnosis of hypertensive disorder of pregnancy will be determined at the time of admission for delivery.

The following investigations are routinely undertaken in the clinical setting once HDP is identified in order to further categorize HDP into more specific diagnoses. These results will be reviewed for each patient to ensure the correct diagnosis has been assigned to the patient. Blood pressure findings as above with none of the findings listed in the table below satisfies a diagnosis of gestational hypertension.

Type of test	Cutoffs	Diagnosis
--------------	---------	-----------

Urine	
 -24-hour protein concentration > 300 mg OR -Protein/Creatinine ratio > 0.3 	Preeclampsia
Serum	
 -Platelets $<100,000/\text{microliter}$ OR -Creatinine $>1.1 \text{ mg/dL}$, or doubling from baseline OR -LFTs $>$ twice the upper limit of normal concentration or twice baseline 	Preeclampsia with severe features
Signs/symptoms: any of the following, if not accounted for by another diagnosis	
 -New-onset, refractory cerebral or visual disturbances -Severe persistent right upper quadrant or epigastric pain unresponsive to medication -Pulmonary edema -Blood pressure ≥ 160 systolic OR ≥ 110 diastolic 	Preeclampsia with severe features
Serum	
 -Platelets $<100,000/\text{microliter}$ AND -Evidence of hemolysis AND -LFTs $>$ twice the upper limit of normal concentration or twice baseline 	Hemolysis, elevated liver enzymes and low platelet count (HELLP) syndrome
Signs/symptoms	New-onset, grand mal seizure, with no history of seizure disorder and not accounted for by any other diagnosis	Eclampsia

De novo postpartum hypertensive disorders of pregnancy will be defined according to the aforementioned criteria and definitions, except for their timing of occurrence after delivery, and in the absence of any antenatal diagnosis of a hypertensive disorder of pregnancy.

2.4 Statistical Analyses

2.4.1 Sample size and statistical power

A case-control study of women who were normotensive at delivery but who were later hospitalized with a diagnosis of severe preeclampsia compared to women who remained normotensive in the postpartum period and women who were diagnosed with preeclampsia in the antenatal period determined that differences in mean arterial blood pressure could be detected following delivery. This retrospective review determined that women who developed de novo postpartum preeclampsia had a greater increase in MAP after delivery than normotensive women (5.0 ± 6.4 mm Hg vs 0.2 ± 6.0 mm Hg, $p < 0.004$).¹³ Though data is scarce on whether a change in MAP can be detected in women with a broader diagnosis of de novo postpartum hypertension, using this reference data to assign an effect size of 5 mm Hg with standard deviation of 6.4 mm Hg and a baseline MAP of 83 mm Hg will provide a conservative estimate of a clinically meaningful change. For a power of 90%, a significance level 5%, and anticipated post-randomization losses of 10%, 41 patients will be needed for each group, or 82 patients total.

2.4.2 Statistical analysis

For analysis of discrete (categorical) data in independent samples, the Chi-squared test or Fisher exact probability test will be utilized. For group comparisons, continuous data that satisfy the assumptions of normality and homoscedasticity (homogeneity of variance) will be analyzed by t-test (for 2 independent samples) or analysis of variance (>2 groups, ANOVA) with post hoc comparisons by Scheffe tests. When possible, continuous data that do not fulfill the aforementioned assumptions will be mathematically transformed (e.g., logarithmic transformation) before performing t-tests or ANOVA. In some cases, data that do not satisfy these assumptions will be analyzed by nonparametric methods [Mann-Whitney U Test (for two independent samples) or Kruskal-Wallis One-Way ANOVA (for more than two independent samples)]. Significant Kruskal-Wallis ANOVAs will be followed by Dunn tests for post hoc analysis. The degree of linear association between variables will be measured by the Pearson product moment correlation coefficient or the Spearman rank-order correlation coefficient and their corresponding tests of significance. Multivariate linear or logistic regression will be utilized where appropriate. In all cases, statistical significance will be assumed when $p < 0.05$. Propensity score analysis will be used as a balancing score as deemed necessary.

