2.3.6 Outcomes

- 1) **Primary outcome:** Our primary outcome will be the difference in mean arterial pressure (MAP) averaged over the 24 hours prior to discharge or the 24 hours prior to antihypertensive therapy initiation (whichever occurs first).
- 2) **Secondary outcomes:** Secondary outcomes will include:
 1. Rates of de novo postpartum preeclampsia – determined at discharge, at 2 and at 6 weeks postpartum
 2. Percentage of recorded blood pressure that are elevated (>140 systolic OR >90 diastolic) – calculated at the time of discharge, at 2 weeks, and at 6 weeks

3. Rates of magnesium sulfate administration – determined at discharge, at 2 and at 6 weeks postpartum
4. Time to discharge
5. Rates of initiation of antihypertensives – determined at discharge, at 2 and at 6 weeks postpartum
6. Rates of severe maternal morbidity (e.g. stroke, seizure, PRES) – determined at 6 weeks postpartum
7. Mean frequency of triage or ED presentation/readmission – determined at 2 and at 6 weeks postpartum
8. Breastfeeding continuation rates – determined at about 2 weeks and at 6 weeks postpartum
9. Neonatal outcomes

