2.5. Anticipated outcomes

The primary outcome will be the difference in the mean arterial blood pressure in the 24 hours prior to discharge or antihypertensive therapy initiation (whichever occurs first) between patients in the study drug group and those in the placebo group. We anticipate that the patients randomized to the study drug will have a significantly lower mean arterial blood pressures than those randomized to placebo. We propose that this will lead to faster normalization of blood pressures, reduce the rate of development of de novo hypertension, specifically preeclampsia, and reduce the morbidity and mortality associated with de novo postpartum hypertension without adverse effect.

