2.7 Timeline

Enrollment is planned to begin in July of 2021, as soon as IRB approval is granted. The sample size required is 41 patients per group for a total of 82 patients. We anticipate that these patients will be successfully recruited into the study within a 12-month period, ending approximately in July of 2022. These patients will need to be followed until 6 weeks postpartum. We anticipate that the study will be completed by August 2022.

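### The unadjusted 5% rule covers all nine secondary outcomes, with no order, adjustment, condition on the primary or exploratory label

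*Combined protocol and SAP*

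**What the plan says.** Section 2.4.2 lists the tests and closes with a threshold that has no exceptions: "In all cases, statistical significance will be assumed when $p < 0.05". The only multiple-comparison procedures named there, Scheffe and Dunn, are for post hoc comparisons among more than two groups. They do nothing across outcomes in a two-arm trial.

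Section 2.3.6 names one primary outcome, mean arterial pressure (MAP) averaged over 24 hours, and nine numbered secondary outcomes. Most of these carry two or three time points, for example "Rates of de novo postpartum preeclampsia – determined at discharge, at 2 and at 6 weeks postpartum".

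Sections 2.2 and 2.5 attach expectations of benefit to several of them. Aim 1 has directional sub-aims on hypertension and preeclampsia, on elevated readings and on hypertension-related visits. Aim 2 does the same for starting antihypertensives, and Aim 3 for severe maternal morbidity. Section 2.5 proposes that lower pressure will "reduce the rate of development of de novo hypertension, specifically preeclampsia, and reduce the morbidity and mortality associated with de novo postpartum hypertension".

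Only the primary is powered (section 2.4.1): "For a power of 90%, a significance level 5%, and anticipated post-randomization losses of 10%, 41 patients will be needed for each group".

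**The concern.** Nothing in the plan separates the primary outcome from the rest when a result is called significant. A reader who applies section 2.4.2 as written can report a significant benefit on any one of nine outcomes, at any listed time, whether or not the MAP result is positive.

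That situation is foreseeable. Section 2.4.3 concedes that early discharge may leave too little time for the diuretic effect to show, and looks to longer follow-up and the secondary outcomes to pick it up. Section 2.6 says the data are meant to inform future guidelines. A single small p-value among many, read as prevention of disease after a null primary, is the error to guard against.

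**Working it through.** **The plan's own figure.** The documents state no error rate across outcomes, so the figure to reproduce is the sample size. Inputs (section 2.4.1): difference 5 mm Hg, SD 6.4 mm Hg, power 90%, alpha 5% (two-sided assumed, since sidedness is not stated), losses 10%.

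- Normal approximation: n = 2 × (1.960 + 1.282)² × 6.4² / 5² = 34.4, so 35 per group; 35/0.9 = 38.9, so 39.
- Noncentral t: 36 per group; 36/0.9 = 40.

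The stated 41 per group is within one or two patients of these. It is not in dispute, and it relates to the primary only.

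**Number of secondary comparisons (section 2.3.6).** In listed order, counting each time point: preeclampsia 3, elevated readings 3, magnesium 3, time to discharge 1, antihypertensive initiation 3, severe morbidity 1, triage or ED visits 2, breastfeeding 2, neonatal outcomes at least 1 (not itemised). The sum is 3+3+3+1+3+1+2+2+1 = 19. With one test per outcome it is 9.

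**Independent tests, no drug effect.** The chance of at least one p < 0.05 in either direction is 1 − 0.95^k. A result favouring the drug uses half of each two-sided 5%, so the chance is 1 − 0.975^k.

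- k = 19: 1 − 0.95^19 = 62%; 1 − 0.975^19 = 38%. Expected nominal positives: 19 × 0.05 = 0.95.
- k = 9: 1 − 0.95^9 = 37%; 1 − 0.975^9 = 20%. Expected: 9 × 0.05 = 0.45.

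**Correlated tests.** Normal test statistics for the 19 comparisons were simulated with 200,000 replicates. The correlations are assumptions.

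| Within outcome over time / between outcomes | Either direction | Favouring drug |
|---|---|---|
| 0.5 / 0.1 | 58% | 32% |
| 0.7 / 0.2 | 51% | 27% |
| 0.8 / 0.4 | 42% | 21% |
| 1.0 / 0.5 | 27% | 13.5% |

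**Rare events.** Most of these outcomes are binary, and section 2.4.2 names chi-squared or Fisher tests. With 41 per group, a two-sided Fisher test of 5 events against 0 gives 2 × C(41,5)/C(82,5) = 0.055, and 6 against 0 gives 2 × C(41,6)/C(82,6) = 0.026. When all events fall in one group, at least six are needed. At a true rate of 1% the actual size of the test is about 0.0% (Fisher) or 0.1% (chi-squared), so severe maternal morbidity adds almost nothing.

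**Simulated null trials.** These had 41 per group, all 19 comparisons and 20,000 replicates. The event rates are assumptions. The low scenario has preeclampsia rising from 3% to 8% and antihypertensive initiation from 5% to 12% by 6 weeks; the high scenario has 10% to 25% and 12% to 28%. Results were 25–48% in either direction and 13–27% favouring the drug. The lowest figures come from Fisher tests in the low scenario with correlated outcomes.

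Taken together, the range is roughly 25–62% in either direction and 13–38% favouring the drug.

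**The case against.** The strongest reply is that the trial names a single primary, labels everything else secondary and powers only MAP, so secondary findings would be read as supportive anyway. Part of this stands. The primary's 5% error is untouched, and the plan nowhere calls the secondary outcomes confirmatory. Sections 2.1 and 2.5 state a purpose and expectations, not claims already made. But the plan does not call them exploratory either, and the threshold in section 2.4.2 makes no distinction. A directional hypothesis in every aim, together with the supporting role given to secondary outcomes in section 2.4.3, makes the supportive reading something the reader must supply.

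A second reply is that 19 is not a firm floor. The listed times may be times of ascertainment, and Aims 1 and 2 frame several of the same outcomes over a single window to 6 weeks. That is fair. The plan does not settle it, which is why 9 and 19 are both carried above.

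A reader might also infer that an ineffective drug has about an even chance of a false efficacy claim. The figures do not support that. Values near 50% count results in either direction, including those that favour placebo. Counting only results that favour furosemide, 19 fully independent tests reach 38%, and plausible correlation and rare events bring this lower. Breastfeeding and neonatal outcomes are also not clearly efficacy outcomes; section 2.2 treats stopping breastfeeding as an adverse effect.

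**Conclusion.** The concern holds as a gap in the decision rule. It is not a flaw in the primary analysis. As written, the plan allows nominal significance on any of 9 to 19 or more secondary comparisons to be reported as a finding, even after a null primary.

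With no drug effect, the chance of at least one such result is roughly 25–62% in either direction and 13–38% favouring the drug. A single two-sided 5% test would allow 5% and 2.5%. The either-direction figure matters too, because Aim 3 includes a hypothesis of no difference in adverse effects that falls under the same threshold.

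The ranges rest on two-sided testing, on the number of tests, and on correlations and event rates that the documents do not give. It would go too far to say that every secondary comparison will be declared significant: each is only tested against 0.05.

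**What to change.** Replace the threshold sentence in section 2.4.2 with wording to this effect: two-sided p < 0.05 is the significance criterion for the primary outcome only; all secondary outcomes and time points are reported as estimates with unadjusted 95% confidence intervals, labelled supportive or exploratory, with no claims of significance.

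If the sponsor wants a formal claim on a secondary outcome, it should fix a short testing order before unblinding. The order is the sponsor's choice, drawn from its stated outcomes and aims. Each outcome should have one named time point and be tested at 5% only if the primary and every earlier step are met. Candidates need one definition: section 2.3.6 lists preeclampsia alone, while Aim 1, sub-aim 1 covers hypertension and preeclampsia.

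The change needs no extra patients and leaves the 82-patient sample size as it is. The cost is that fewer outcomes can be called significant.

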2.4.3 Strengths and limitations

Strengths of our study include a randomized control design, as well as a large cohort of patients who will be eligible for enrollment. CUIMC has 9 obstetric clinics which annually experience 27,612 deliveries, of which only 2,853 would be excluded based on an antenatal diagnosis of HDP.

Project limitations include potential fear among patients of a medication that is not standardly used in postpartum management that could limit enrollment. Additionally, patients are being discharged earlier than prior to the start of the COVID-19 pandemic, which would limit the amount of blood pressure data that can be collected and may limit the amount of time necessary to be able to see the effect of the diuresis; however, extended follow up and secondary outcomes included in the analysis, particularly review of logs at 10-14 days postpartum may assist in capturing the effect of the intervention after discharge.

2.5. Anticipated outcomes

The primary outcome will be the difference in the mean arterial blood pressure in the 24 hours prior to discharge or antihypertensive therapy initiation (whichever occurs first) between patients in the study drug group and those in the placebo group. We anticipate that the patients randomized to the study drug will have a significantly lower mean arterial blood pressures than those randomized to placebo. We propose that this will lead to faster normalization of blood pressures, reduce the rate of development of de novo hypertension, specifically preeclampsia, and reduce the morbidity and mortality associated with de novo postpartum hypertension without adverse effect.

2.6 Significance

There are several knowledge gaps in the postpartum management of women with pregnancy-related hypertension. Specifically, no management recommendations or interventions for women at risk for developing de novo postpartum hypertension have been described, despite the evidence for their high risk of morbidity. These knowledge gaps have important clinical implications and answering them will provide valuable information regarding the low-cost interventions to reduce morbidity. The overall goal of this project is to collect empiric data for future guidelines on the use of diuretic therapy among postpartum women at risk for de novo postpartum hypertension.

2.7 Timeline

Enrollment is planned to begin in July of 2021, as soon as IRB approval is granted. The sample size required is 41 patients per group for a total of 82 patients. We anticipate that these patients will be successfully recruited into the study within a 12-month period, ending approximately in July of 2022. These patients will need to be followed until 6 weeks postpartum. We anticipate that the study will be completed by August 2022.

2.8 Environment

The Columbia Department of OB/GYN brings substantial experience and skill in organizing and participating in clinical research. We have a strong track record in all areas of collaborative research including protocol design, implementation, data analysis and dissemination of findings. Our productivity is facilitated by a number of factors: (1) A critical mass of academic full time faculty with sufficient time and skill to perform clinical research, (2) the presence of a diverse patient population willing to participate in research initiatives, and (3) an established research environment in which clinicians accept participation in research initiatives as a major role of a teaching institution. This has led to a longstanding reputation for excellence in clinical research.

Of utmost importance is our research infrastructure with a proven record of success, which is embedded in the elaborate system of prenatal clinics and obstetric services and complemented by our large and diverse population of over 6,600 deliveries per year, advanced support systems,

strong division of Neonatology, outstanding follow-up programs and a patient population proven to be receptive to participation in research. The research staff is trained and certified in Good Clinical Practice, HIPPA, Blood Borne Pathogen Handling, and IATA Shipping Regulations. All staff is capable of collecting patient samples, cord blood and placental processing (including RNA, proteomics and DNA). Our research staff of over 25 individuals are trained and certified in each ongoing project. This maximizes efficiencies in recruitment and the performance of study procedures and also allows staff to share the responsibility of on-call coverage.

The Department of OB/GYN maintains a centralized administrative research office that manages pre- and post-award grant administration, and oversees roughly \$10 million in sponsored research funding annually. The Office analyzes, monitors, and evaluates the Department's research activities including all federal and non-federal sponsored awards and contracts. They ensure the efficient, cost-effective administration and financial management and ensure compliance with internal and external policies and procedures.

2.10 Risks, Benefits, and Monitoring

2.10.1 Risks

Lasix (furosemide) is in a class of drugs call diuretics and is commonly used to treat edema (swelling) and hypertension. Lasix is considered safe for use in adults and pediatric patients. If given in excessive amounts, Lasix can cause dehydration and electrolyte imbalances. Other possible side effects include dryness of mouth, thirst, weakness, lethargy, drowsiness, restlessness, muscle pains or cramps, muscular fatigue, hypotension, oliguria, tachycardia, arrhythmia, or gastrointestinal disturbances such as nausea and vomiting. Increases in blood glucose and alterations in glucose tolerance tests (with abnormalities of the fasting and 2-hour postprandial sugar) have been observed, and rarely, precipitation of diabetes mellitus has been reported.

In patients with severe symptoms of urinary retention (because of bladder emptying disorders, prostatic hyperplasia, urethral narrowing), the administration of furosemide can cause acute urinary retention related to increased production and retention of urine. Thus, these patients require careful monitoring, especially during the initial stages of treatment.

Lasix is contraindicated in patients with anuria and in patients with a history of hypersensitivity to furosemide. Therefore, if you do not produce urine or if you have ever had an allergic reaction to furosemide, you will not be able to participate in the study.

A very small amount of Lasix may pass to the baby through breast milk. Lasix may also inhibit lactation.

Since the use of the study drug is investigational, there may be other risks that are unknown. These may be minor or severe. They may find out new risks while the study is going on. If this happens, the research staff will tell the participants any new information, whether it may affect her, and what, if anything, to expect.

Another risk of taking part in this study is the possibility of a loss of confidentiality. All efforts will be made to maintain confidentiality, including storage of data on secure servers and deidentification of data after it is collected.

2.10.2 Benefits

Participants may benefit from a reduction in blood pressure that could lead to lower rates of serious complications (e.g. seizure or stroke) as a result of participation in this study. There is, however, no guarantee that they will benefit from participation in this study. Information learned from the study may help other people in the future.

